9 STATISTICS

9.1 Analysis Populations

The Intent-to-Treat (ITT) Population is defined as all subjects randomized. Subjects in this population will be analyzed according to the treatment group to which they were assigned at randomization. The ITT Population will be used for efficacy analyses.

The Per-Protocol (PP) Population is a subset of the ITT Population and will include subjects that have at least 1 post-dose efficacy evaluation and do not have major protocol deviations.

The Safety Population is defined as all randomized subjects who received at least 1 dose of study drug. Subjects in this population will be analyzed according to the study drug they actually received. The Safety Population will be used for the analysis of safety endpoints.

9.2 Statistical Methods

Additional details of the statistical analyses will be provided in the Statistical Analysis Plan, which will be finalized prior to database lock.

9.2.1 Analysis of Efficacy

Continuous efficacy endpoints will be analyzed using an analysis of variance model with effects for treatment and disease severity as factors.

Binary efficacy endpoints will be analyzed using a Cochran-Mantel-Haenszel test stratified by disease severity.

For all efficacy endpoints that do not include death as a possible outcome, data from subjects who die prior to Day 28 will be imputed at Day 28 based on the worst outcome.

All efficacy analyses will be performed using the ITT Population. The efficacy analyses will be repeated on the PP Population.

9.2.2 Pharmacodynamic Analysis

Pharmacodynamic endpoints will be summarized descriptively.

9.2.3 Pharmacokinetic Analysis

PK concentrations will be summarized descriptively by treatment group and by day and time of sample collection post dose.

9.2.4 Analysis of Safety

The safety endpoint data will be summarized for the Safety Population. AEs will be coded using the latest version of the Medical Dictionary for Regulatory Activities (MedDRA). AEs and SAEs will be summarized by overall number of AEs, severity, and relationship to study drug per treatment group. Summaries will be presented by MedDRA system organ class and preferred term using frequency counts and percentages by treatment group and overall.

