2 STUDY OBJECTIVES

2.1 Primary Objectives

The primary objectives of this study are to assess the safety and efficacy of razuprotafib in subjects with moderate to severe COVID-19.

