8.7 Safety Assessments

The safety endpoints include the following:

- Number of subjects with any SAE; and
- Number of subjects with any treatment-emergent AE.

Safety will be determined by evaluating clinical laboratory findings (blood chemistry, hematology, and coagulation), vital signs (blood pressure, heart rate, SpO₂ [for non-ventilated subjects only], and respiratory rate), 12-lead electrocardiograms, and AEs reported during the study.

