3.4 Efficacy Assessment

All efficacy analysis will be performed using the ITT Population. Selected endpoints will be repeated on the FA and PP Populations. In addition, the efficacy analyses will be analyzed for pooled razuprotafib doses and placebo.

Additional analyses to understand safety and efficacy variables further may be carried out and will be labeled as post-hoc analyses.

3.4.1 *Efficacy Endpoints*

The following parameters will be analyzed using Cochran-Mantel-Haenszel (CMH) test stratified by disease severity:

- Proportion of subjects alive and free of respiratory failure at Day 28;
- Proportion of subjects alive and free of respiratory failure at Day 7;

All results will be summarized descriptively by treatment arm and expressed as proportions, along with corresponding 95% CI of the difference between response rates, and p-values. The 95% CI will be constructed using the normal approximation method.

Additional Analysis may be considered by incorporating other covariate adjustments into the analysis.

Respiratory failure will be defined as subjects who are on invasive mechanical ventilation; are receiving oxygen delivered by high-flow nasal cannula (heated, humidified, oxygen delivered via reinforced nasal cannula at flow rates >20 L/min with fraction of delivered oxygen ≥ 0.5) noninvasive positive pressure ventilation or extracorporeal membrane oxygenation; or have a

clinical diagnosis of respiratory failure (ie, clinical need for 1 of the preceding therapies, but preceding therapies not able to be administered in setting of resource limitation). Subject who die prior to the study timepoint (Day 7 or Day 28) will be imputed based on the worst outcome. Other missing responses will be imputed using a multiple imputation (MI) method under the assumption of missing at random (MAR).

Sensitivity Analysis

- All missing responses will be considered as non-responders and which will be imputed taking the worst case approach.
- The analysis will be repeated on FA and PP Populations.

The following parameters will be analyzed using the CMH test as stated above:

- Proportion of subjects alive and not requiring invasive mechanical ventilation at any time through Day 28;
- Proportion of subjects who improve by ≥ 2 categories on the NIAID 8-point ordinal scale from baseline to Day 7 and baseline to Day 28;
- Proportion of subjects who worsen by ≥ 2 categories on the NIAID 8-point ordinal scale from baseline to Day 7 and baseline to Day 28;

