3.6.1 Adverse Events (AEs)

AEs, which include clinical laboratory test variables, will be monitored and documented from the time of the first dose of study drug until Day 28. All AEs will be coded to system organ class and preferred term using MedDRA version 23.0. Treatment-emergent adverse events (TEAEs) will be defined as an event that occurs on or after the first dose of study drug.

An overview of AEs will be provided including counts and percentages of subjects and event counts with the following:

- Any TEAEs (Overall, by maximum severity)
- Any study drug related TEAEs
- Any treatment-emergent serious AEs (TESAEs)

- Any TEAEs leading to discontinuation of study drug
- Any TEAEs leading to death

Counts and percentages of subjects and event counts will also be presented by system organ class and preferred term for each of the categories in the overview.

All AEs will be displayed in listings. In addition, listings will be presented specifically for SAEs and TEAEs leading to discontinuation of study drug.

3.6.2 *Clinical Laboratory Tests*

Values and changes from baseline of clinical laboratory variables for blood chemistry, hematology, and coagulation will be summarized using descriptive statistics by treatment group and time point. The number of available observations and out-of-range values (absolute and in percentage) will also be presented by treatment group. Clinical Laboratory data will be listed.

3.6.3 *Vital Signs*

Vital signs will include blood pressure, heart rate, SpO2 (for non-ventilated subjects only), and respiratory rate. Temperature will be measured at Screening only.

Values, changes from baseline, changes from pre-dose for each TID dose of vital signs will be summarized using descriptive statistics by treatment group and time point. Vital signs will be listed.

3.6.4 *Electrocardiograms*

Values and changes from baseline of electrocardiograms data will be summarized using descriptive statistics by treatment group and time point (baseline and Day 7). The overall interpretation will be summarized by counts and percentages by treatment group and total. 12-lead electrocardiograms data will be listed.

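### Safety is a joint primary objective, but the two named safety endpoints get no prespecified difference from placebo, confidence interval or pooled-razuprotafib column

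*Protocol*

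**What the plan says.** Protocol 2.1 puts safety on the same footing as efficacy: "The primary objectives of this study are to assess the safety and efficacy of razuprotafib in subjects with moderate to severe COVID-19". SAP 2.1.1 repeats this. Protocol 8.7 and SAP 2.3.3 name two safety endpoints: the number of subjects with an SAE, and "Number of subjects with any treatment-emergent AE".

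For adverse events, Protocol 9.2.4 plans this display: "Summaries will be presented by MedDRA system organ class and preferred term using frequency counts and percentages by treatment group and overall". SAP 3.6.1 is similar: "An overview of AEs will be provided including counts and percentages of subjects and event counts with the following". The list that follows covers TEAEs overall and by maximum severity, drug-related TEAEs, serious TEAEs, and TEAEs leading to discontinuation or death. Neither section mentions a difference from placebo, a confidence interval or a group that combines the razuprotafib doses.

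Efficacy is handled differently. SAP 3.4 says: "In addition, the efficacy analyses will be analyzed for pooled razuprotafib doses and placebo". SAP 3.4.1 gives the CMH and ANOVA endpoints a between-group difference with a 95% confidence interval and a p-value.

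The only route to further safety analysis is also in SAP 3.4: "Additional analyses to understand safety and efficacy variables further may be carried out and will be labeled as post-hoc analyses".

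**The concern.** In patients hospitalized with COVID-19, the disease itself will produce SAEs. An arm's SAE percentage therefore says little about the drug until it is set against placebo, and the size and uncertainty of that difference are what a reader needs. The plan prespecifies both for most efficacy endpoints but for neither named safety endpoint.

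The groups are small and have no formal sample-size basis (Protocol 9.2.5). Similar percentages side by side, without an interval, can be read as reassurance when the data also allow a substantial excess. An interval calculated later would carry the post hoc label, for an endpoint that serves a primary objective.

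**Working it through.** The documents give no precision or power figure for safety, so there is no planned number to reproduce. The check asks how wide the missing interval would be.

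**Inputs from the documents**
- Each Part 1 step has about 30 subjects at 1:1:1 (Protocol 9.2.5): 30/3 = 10 per arm, or 20 v 10 with both doses combined.
- Part 2 has about 120 subjects at 1:1:1 (Protocol 9.2.5): 120/3 = 40 per arm, or 80 v 40 with both doses combined. With one dose at 2:1 the arms are 80 v 40 from the start.

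**Assumption.** No SAE or TEAE rate is given. I use 10%, 20% and 30%, equal in both groups, for illustration only. Each step and part is taken by itself.

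**Formula.** Half-width = 1.96 × √[p(1−p) × (1/n₁ + 1/n₀)]. This is the normal approximation that SAP 3.4.1 uses for binary efficacy endpoints.

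Example, 40 v 40 at 20%: 1.96 × √(0.16 × 0.05) = 1.96 × 0.0894 = 0.175.

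| Comparison | 1/n₁ + 1/n₀ | 10% | 20% | 30% |
|---|---|---|---|---|
| Part 1 step, one dose, 10 v 10 | 0.2000 | ±26.3 | ±35.1 | ±40.2 |
| Part 1 step, doses combined, 20 v 10 | 0.1500 | ±22.8 | ±30.4 | ±34.8 |
| Part 2, one of two doses, 40 v 40 | 0.0500 | ±13.1 | ±17.5 | ±20.1 |
| Part 2, doses combined or single dose at 2:1, 80 v 40 | 0.0375 | ±11.4 | ±15.2 | ±17.4 |

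Entries are percentage points. The 10 v 10 row shows order of magnitude only: with 1 to 3 expected events per arm, the normal approximation is poor. An exact one-arm figure points the same way: for 0 events in 10, the upper Clopper-Pearson 95% limit is 1 − 0.025^(1/10) = 30.8%.

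**What this means in a table.** If both arms of a 40 v 40 comparison show 20% (8 of 40 each), the interval runs from −17.5 to +17.5 points. The planned output would show two equal percentages and nothing more.

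**What pooling adds.** Going from 40 v 40 to 80 v 40 multiplies the variance by 0.0375/0.05 = 0.75, and the width by √0.75 = 0.87. The interval narrows by about 13%. With a single dose at 2:1, a pooled column adds nothing within Part 2.

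**The case against.** Descriptive AE reporting is common in Phase 2. The endpoints are worded as numbers of subjects, so counts by arm report exactly what is named. Safety decisions during the trial rest on DRC review (Protocol 3.2 and 4.4.2), not on a final interval. All of this is fair. It argues against adding hypothesis tests, but not against adding an estimate.

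A reader might infer more than the documents support:

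- **That serious harm is never contrasted with placebo.** SAP 3.4.1 puts all-cause mortality at Day 7 and Day 28 under the CMH analysis, with a difference and interval, and SAP 3.4 repeats it for pooled doses. Worsening on the NIAID scale and survival without invasive ventilation are treated the same way. These are ITT efficacy endpoints. They cover grave outcomes but not SAEs or TEAEs as such.
- **That safety is only counted.** SAP 3.6.2 to 3.6.4 give values and changes from baseline for laboratory tests, vital signs and ECGs. For vital signs this includes change from the pre-dose value at each dose. The gap concerns the adverse-event endpoints.
- **That all efficacy endpoints get a difference and interval.** Time to NIAID grade 6 to 8, the NIAID category counts and time to prehospitalization oxygen requirement are descriptive only.
- **That the overall column misleads.** It is nowhere offered as a contrast, and the arm columns stand beside it. Protocol 9.2.4 does not define it, and SAP 3.6.1 does not use it for AEs.
- **That the trial cannot state what excess it has ruled out.** Anyone with the arm counts can add the dose columns and compute a crude difference and interval. What is missing is the prespecified status and the printed result.

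**Conclusion.** The point holds as a gap in prespecified estimation. For any SAE and any TEAE, the plan has no razuprotafib-minus-placebo difference, no interval and no pooled column, although safety is a joint primary objective and the CMH and ANOVA efficacy endpoints have them. No passage contradicts another, and no information is lost. The consequence is that the excess risk compatible with the data will be reported only if someone calculates it afterwards.

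The unreported uncertainty is large: roughly 26 to 40 points either way for one dose in a Part 1 step, 13 to 20 for one of two doses in Part 2, and 11 to 17 at 80 v 40. These figures rest on assumed event rates of 10% to 30%, equal arms, and a normal approximation that is rough in Part 1. Most of the value lies in the difference and its interval. Pooling is a modest extra, and only where more than one dose is tested. This is a worthwhile, low-cost improvement and not a flaw that undermines the trial.

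**What to change.** In Protocol 9.2.4 and SAP 3.6.1:

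1. Add a pooled-razuprotafib column beside each dose and placebo wherever more than one dose is tested.
2. For any SAE, any TEAE and Grade 3 or higher TEAE, report the risk difference versus placebo, per dose and pooled, with a 95% score-type interval (Miettinen-Nurminen) and no p-value.
3. Leave the interval unstratified in Part 1. With 10 per arm and up to about half moderate, strata would hold about 5 per arm, and sentinel randomization is not stratified (Protocol 5.3). Stratify by disease severity in Part 2 only.

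The cost is a few sentences and some table columns. No new data are needed, since AE severity is already graded and tabulated. The one downside is that pooling can dilute a harm confined to the top dose, so the per-dose rows must stay.

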9.2.5 Sample Size Determination

Part 1 will include approximately 60 subjects. In Part 1, Step 1, approximately 30 subjects (including the 6 sentinel subjects) will be randomized to 1 of 3 treatment groups (razuprotafib 10 mg TID, razuprotafib 20 mg TID, or placebo TID) in a 1:1:1 ratio. In Part 1, Step 2, approximately 30 subjects (including the 6 sentinel subjects) are planned to be randomized to 1 of 3 treatment groups (razuprotafib 20 mg TID, razuprotafib 30 mg TID, or placebo TID) in a 1:1:1 ratio. If it is decided that only 1 dose level will be evaluated in Part 1, Step 2, then subjects will be randomized to 1 of 2 treatment groups (razuprotafib or placebo) in a 2:1 ratio (razuprotafib:placebo). No formal statistical assessment for sample size determination has been performed for Part 1. The sample size is considered adequate to provide the necessary data to evaluate the objectives for Part 1.

Part 2 will include approximately 120 subjects. Subjects will be randomized to 1 of the treatment groups (dose 1 razuprotafib TID, dose 2 razuprotafib TID [optional], or placebo TID) in a 1:1:1 ratio (or a 2:1 ratio [razuprotafib:placebo] if only 2 treatment groups). No formal statistical assessment for sample size determination has been performed for Part 2. The sample size is considered adequate to provide the necessary data to evaluate the objectives for Part 2.

10 DATA MANAGEMENT AND RECORD KEEPING

10.1 Data Management

10.1.1 Data Handling

Data will be recorded at the site on eCRFs and reviewed by the CRA during monitoring visits. The CRAs will verify data recorded in the EDC system with source documents. All corrections or changes made to any study data must be appropriately tracked in an audit trail in the EDC system. An eCRF will be considered complete when all missing, incorrect, and/or inconsistent data have been accounted for.

10.1.2 Computer Systems

Data will be processed using a validated computer system conforming to regulatory requirements.

10.1.3 Data Entry

Data must be recorded using the EDC system as the study is in progress. All site personnel must log into the system using their secure username and password in order to enter, review, or correct study data. These procedures must comply with Title 21 of the Code of Federal Regulations (21 CFR Part 11) and other appropriate international regulations. All passwords will be strictly confidential.

10.1.4 Medical Information Coding

For medical information, the following thesauri will be used:

- MedDRA (latest) for medical history and AEs; and
- World Health Organization Drug Dictionary for prior and concomitant medications.

10.1.5 Data Validation

Validation checks programmed within the EDC system, as well as supplemental validation performed via review of the downloaded data, will be applied to the data in order to ensure accurate, consistent, and reliable data. Data identified as erroneous, or data that are missing, will be referred to the investigative site for resolution through data queries.

The eCRFs must be reviewed and electronically signed by the Investigator.

10.2 Record Keeping

Records of subjects, source documents, monitoring visit logs, eCRFs, inventory of study product, regulatory documents, and other Sponsor correspondence pertaining to the study must be kept in the appropriate study files at the site. Source data are defined as all information in original records and certified copies of original records of clinical findings, observations, or other activities in a clinical study necessary for the evaluation and reconstruction of the clinical study. Source data are contained in source documents (original records or certified copies). These records will be retained in a secure file for the period as set forth in the Clinical Study Agreement. Prior to transfer or destruction of these records, the Sponsor must be notified in writing and be given the opportunity to further store such records.

10.3 End of Study

The end of the study (“study completion”) is defined as the date of the last protocol-specified visit/assessment (including telephone contact) for the last subject in the study.

11 INVESTIGATOR REQUIREMENTS AND QUALITY CONTROL

11.1 Ethical Conduct of the Study

GCP is an international ethical and scientific quality standard for designing, conducting, recording, and reporting studies that involve human subjects. Compliance with this standard provides public assurance that the rights, safety, and wellbeing of study subjects are protected, consistent with the principles that have their origin in the Declaration of Helsinki, and that the clinical study data are credible.

11.2 Institutional Review Board

The Institutional Review Board (IRB) will review all appropriate study documentation in order to safeguard the rights, safety, and wellbeing of subjects. The study will only be conducted at sites where IRB approval has been obtained. The protocol, Investigator's Brochure, ICF, advertisements (if applicable), written information given to the subjects, safety updates, annual progress reports, and any revisions to these documents will be provided to the IRB by the Investigator.

Federal regulations and ICH Guidelines require that approval be obtained from an IRB prior to participation of subjects in research studies. Prior to study onset, the protocol, any protocol amendments, ICFs, advertisements to be used for subject recruitment, and any other written information regarding this study to be provided to a subject must be approved by the IRB.

No drug will be released to the site for dosing until written IRB authorization has been received by the Sponsor.

11.3 Informed Consent

The ICF and any changes to the ICF made during the course of the study must be agreed to by the Sponsor or designee and approved by the IRB prior to its use and must be in compliance with all ICH GCP, local regulatory requirements, and legal requirements.

The Investigator must ensure that each study subject or their LAR is fully informed about the nature and objectives of the study and possible risks associated with participation and must ensure that the subject has been informed of his/her rights to privacy. The Investigator will obtain written informed consent from each subject or LAR before any study-specific activity is performed and should document in the source documentation that consent was obtained prior to enrollment in the study. The original signed copy of the ICF must be maintained by the Investigator and is subject to inspection by a representative of the Sponsor, their representatives, auditors, the IRB, and/or regulatory agencies. A copy of the signed ICF will be given to the subject or LAR. Subjects consented via a LAR will be re-consented at the earliest opportunity they are able to provide consent.

11.4 Study Monitoring Requirements

It is the responsibility of the Investigator to ensure that the study is conducted in accordance with the protocol, Declaration of Helsinki, ICH GCP, and applicable regulatory requirements, and that valid data are entered into the eCRFs.

To achieve this objective, the monitor's duties are to aid the Investigator and, at the same time, the Sponsor in the maintenance of complete, legible, well organized, and easily retrievable data. Before the enrollment of any subject in this study, the Sponsor or their designee will review with

the Investigator and site personnel the following documents: protocol, Investigator's Brochure, eCRFs and procedures for their completion, informed consent process, and the procedure for reporting SAEs.

The Investigator will permit the Sponsor or their designee to monitor the study as frequently as deemed necessary to determine that data recording and protocol adherence are satisfactory. During the monitoring visits, information recorded on the eCRFs will be verified against source documents and requests for clarification or correction may be made. After the eCRF data are entered by the site, the CRA will review the data for safety information, completeness, accuracy, and logical consistency. Computer programs that identify data inconsistencies may be used to help monitor the clinical study. If necessary, requests for clarification or correction will be sent to Investigators. The Investigator and his/her staff will be expected to cooperate with the monitor and provide any missing information, whenever possible.

All monitoring activities will be reported and archived. In addition, monitoring visits will be documented at the investigational site by signature and date on the study-specific monitoring log.

